2.2 DISPOSITION OF PATIENTS

This section describes patient disposition for both patient study status and the patient analysis populations.

Screened patients will be defined as any patient who has signed the informed consent form.

Randomized patients consist of all patients who have had a treatment kit number allocated and recorded in the IRT database, regardless of whether the treatment kit was used.

Patients treated without being randomized will not be considered as randomized and will not be included in any efficacy population. The efficacy results for the pediatric patients who are enrolled directly in the open-label avalglucosidase alfa long term follow-up phase will be listed.

For patient study status, the total number of patients in each of the following categories will be presented in the PAP clinical study report using summary table:

- Screened patients,
- Screen failure patients and reasons for screen failure (if data is available),
- Nonrandomized but treated patients (if applicable),
- Randomized patients,
- Randomized but not treated patients,
- Randomized and treated patients,
- Number and percentage of patients who did not complete PAP treatment period, with corresponding reasons,
- The total number of patients in each of the following categories will be presented in the ETP clinical study report using summary table.
- Patients who continue into ETP,
- Patients who did not complete ETP,
- Pediatric patients enrolled directly in the open-label avalglucosidase alfa long term follow-up phase
- Number and percentage of patients who did not complete ETP treatment, with corresponding reasons (will be included in final study report only),
- Number and percentage of patients who did not complete ETP follow-up, with corresponding reasons (will be included in final study report only).

For all categories of patients (except for the screened and nonrandomized categories) the summaries will be provided by randomized treatment, and percentages will be calculated using the number of randomized patients as the denominator.

All critical or major deviations potentially impacting efficacy analyses, randomization, and drug-dispensing irregularities, and other major or critical deviations will be summarized in tables giving numbers and percentages of deviations by treatment group.

Additionally, the analysis populations for safety, efficacy, and PK will be summarized in a table by number of patients on the randomized population.

- Efficacy population: modified intent-to-treat (mITT) population/per-protocol population,
- Safety population,
- PK population.

2.2.1 Randomization and drug dispensing irregularities in PAP

Randomization and drug-dispensing irregularities occur whenever:

- A randomization is not in accordance with the protocol-defined randomization method, such as a) an ineligible patient is randomized, b) a patient is randomized based on an incorrect stratum, c) a patient is randomized twice;
OR,
- A patient is dispensed an IMP kit not allocated by the protocol-defined randomization, such as a) a patient at any time in the study is dispensed a different treatment kit than as randomized (which may or may not contain the correct-as-randomized IMP), or b) a nonrandomized patient is treated with IMP reserved for randomized patients.

Randomization and drug-dispensing irregularities will be monitored throughout the study and reviewed on an ongoing basis.

All randomization and drug-dispensing irregularities will be documented in the clinical study report. Whether any of these constitute a major protocol deviation is deferred to the decision by the clinical team before the database lock. Nonrandomized, treated patients will be described separately.

Randomization and drug-dispensing irregularities to be prospectively identified include but are not limited to:

Table 13 - Randomization and drug allocation irregularities

Randomization and drug allocation irregularities
Kit dispensation without IRT transaction
Erroneous kit dispensation
Kit not available
Randomization by error
Patient randomized twice
Stratification error
Patient switched to another site

2.3 ANALYSIS POPULATIONS

The randomized population includes any patient who has been allocated to a randomized treatment regardless of whether the treatment kit is used. The pediatric patients who are enrolled directly in the open-label avalglucosidase alfa long term follow-up phase will be included in the ETP population and will not be included in the randomized population. Listings will be generated based on enrolled population which includes all randomized population and pediatric patients who are enrolled directly in the open-label phase.

2.3.1 Efficacy populations

Patients treated without being randomized will not be considered randomized and will not be included in any efficacy population.

2.3.1.1 Modified intent-to-treat population

The mITT population will include randomized patients who receive at least 1 infusion (partial or total). The mITT population will be used for all efficacy analyses unless otherwise specified. Analyses using the mITT population will be performed according to the treatment arm allocated by randomization, regardless of the actual treatment received.

2.3.1.2 Per-protocol population

The per-protocol (PP) population will consist of mITT patients who meet all of the following criteria:

- Meet all of the inclusion and exclusion criteria (See protocol Section 7.1 and 7.2),
- Received at least 80% of planned # of doses,
- Having a valid FVC (% predicted) assessment at Week 49,
- No major protocol deviations that will potentially impact on primary study objective.

The following criteria have been identified a priori as major deviations that will potentially impact on primary study objective. Additional major deviations maybe identified during the study. These will be reviewed and approved by sponsor prior to database lock and unblinding of treatment assignment.

- Patient receives doses 2 times higher than the protocol planned dose,
- Patient receives treatment different from the randomized assignment during the PAP,
- The treatment assignment is unblinded before the planned unblinding (completion of PAP) not due to safety reasons specified in the protocol.

The reason for excluding patients from the PP population will be summarized by randomized treatment group and presented in data listing.

PP population will be used for sensitivity analysis of the primary efficacy endpoint in PAP only.

2.3.2 Safety population

The safety population will be analyzed according to treatment received. In PAP, safety population includes randomized patients who receive at least 1 infusion in PAP. In ETP, safety population includes patients who receive at least 1 infusion in ETP and includes pediatric patients who are directly enrolled to ETP. Overall safety of avalsuglucosidase alfa will be based on patients who receive at least 1 infusion during either PAP or ETP.

- Nonrandomized but treated patients will not be part of the safety population in PAP; however, their safety data will be presented separately in PAP.
- Randomized patients for whom it is unclear whether they took the IMP will be included in the safety population as randomized.

2.3.3 Additional analysis populations

The ETP population will consist of patients who receive at least one avalu glucosidase alfa dose during the ETP.

The pharmacokinetic population will consist of patients from safety population in PAP who have evaluable drug concentration data.

The pharmacodynamics or pharmacogenetic analysis population for the parameter of interest will consist of mITT patients and have evaluable pharmacodynamic data for the parameter of interest.

The ADA evaluable population will consist of patients from safety population who have at least one ADA sample taken post-baseline after drug administration that is appropriate for ADA testing with a reportable result. Patients with missing or non-reportable baseline samples and reportable post-baseline samples will be considered as evaluable.

2.4 STATISTICAL METHODS

Unless otherwise specified, efficacy analyses will use the mITT population, where patients will be considered to be in the treatment group to which they were randomized. Corresponding supportive analysis will be performed for PP population as well. Safety analyses will use the safety population, where patients who receive at least one infusion of avalu glucosidase alfa in PAP will be assigned to the avalu glucosidase alfa arm for the PAP safety analysis purposes.

For all analyses, the avalu glucosidase alfa treatment group will be compared to the alglucosidase alfa group. While the primary comparison of interest is at 12 months (49 weeks), all summary statistics will be computed and displayed by treatment group and each scheduled assessment time as well. Summary statistics for continuous variables will minimally include n, mean, SD, minimum, median, and maximum. For categorical variables, frequencies and percentages will be presented. Graphical displays will be provided as appropriate.

2.4.1 Demographics and baseline characteristics

Continuous data will be summarized using the number of available observations, mean, SD, median, minimum, and maximum for each treatment group. Categorical and ordinal data will be summarized using the number and percentage of patients in each treatment group. Denominators for the percentages will be based on the analysis population used, unless otherwise specified.

Demographics and baseline disease characteristics as described in [Section 2.1.1](#) will be summarized by randomized treatment group and pooled treatment groups in mITT population. Summaries for the safety population will be included in the appendices if the size of the safety

population is different (>10%) from the size of that in the primary analysis population for any treatment group, or if the randomized treatment for any patient is different from the actual treatment received.

Medical history will be summarized by body system and treatment group and overall in mITT population.

Baseline values of the key efficacy parameters such as FVC, 6MWT, MIP, MEP, lower extremity HHD, QMFT and SF-12, will be summarized by randomized treatment group and pooled treatment group in mITT population. Baseline values of additional secondary efficacy parameters will be summarized along with each efficacy analysis. GAA gene and ACE allele genotype status will also be summarized.

P-values on demographic and baseline characteristic data will not be calculated.

No specific description of the safety parameters will be provided at baseline. If relevant, the baseline values will be described along with each safety analysis.

2.4.2 Prior or concomitant medications

Prior medications will be defined as medications that are taken in the 30 days before the first infusion of study drug. Concomitant medications will be defined as medications that are taken after the first infusion of study drug. If a drug is started before first infusion of study drug but continues after the first infusion of the study drug, it is considered prior as well as concomitant.

Medications will be summarized by treatment group according to the WHO-DD dictionary, considering the first digit of the anatomic and therapeutic category (ATC) class and the first 3 digits of the ATC class (therapeutic category). All ATC codes corresponding to a medication will be summarized, and patients will be counted once in each ATC category (anatomic or therapeutic) linked to the medication. Therefore, patients may be counted several times for the same medication. Prior and concomitant medications will be summarized separately and will use mITT population.

In ETP analyses, prior and concomitant medications will also be summarized for the ETP treatment epoch among the ETP population, as well as for the overall avalsuglucosidase alfa treatment period among patients who receive at least one dose of avalsuglucosidase alfa in either PAP or ETP.

2.4.3 Extent of investigational medicinal product exposure and compliance

2.4.3.1 Extent of investigational medicinal product exposure

The extent of study drug exposure will be assessed by the duration of study drug exposure, number of infusions, and amount of dose received. The extent of study drug exposure will be summarized in safety population. Patient year as calculated from the first infusion date to the date of last follow-up visit will be summarized by treatment.

Duration of study drug exposure is defined below:

For PAP

- Duration of IMP exposure is defined as the first dose date in the ETP (or 14 days after the last dose date in PAP if the patient is not continuing in ETP)—first dose date in PAP, regardless of unplanned intermittent discontinuations.
- For ETP,
- Duration of IMP exposure is defined as 14 days after last dose in ETP—first dose date in the ETP, regardless of unplanned intermittent discontinuations. This is defined only for those patients treated in ETP.
- For the overall treatment duration,
- Duration of avalu glucosidase alfa total exposure is defined as 14 days after last avalu glucosidase alfa dose in study—first avalu glucosidase alfa dose date in the study.

The duration of IMP exposure will be summarized descriptively as a quantitative variable (number, mean, SD, median, minimum, and maximum), as well as categorical variable (eg, <3 months, 3-6 months, 6-9 months, 10-12 months, >12 months for PAP).

The cumulative dose information for PAP will be assessed by the total number of infusions received in PAP, as well as total amount of IMP in ml (if this information is available from the database) received in PAP. These data will be summarized descriptively.

The cumulative dose information for avalu glucosidase alfa during the overall treatment duration will be assessed by the total number of avalu glucosidase alfa infusions received during the overall treatment duration, as well as the total amount of avalu glucosidase alfa in ml received during the overall treatment duration. These data will be summarized descriptively by randomized treatment group (Avalu glucosidase alfa PAP/valu glucosidase alfa ETP vs. avalu glucosidase alfa PAP/valu glucosidase alfa ETP), among the safety population.

2.4.3.2 Compliance

Treatment compliance for PAP will be summarized descriptively as quantitative variable using mITT population and randomized treatment group. Compliance is calculated as the total amount of drug actually taken by a patient divided by the total amount of drug expected to be taken multiplied by 100. The number and percentage of patients with noncompliance (missed 2 or more consecutive infusions not for safety cause, or missed $\geq 20\%$ of total doses in the 49-week PAP), and by reasons will be provided.

Treatment compliance for ETP and overall study period will be summarized similarly.

2.5 ANALYSES OF EFFICACY ENDPOINTS

All efficacy endpoints will be summarized descriptively at each study visit, as well as the last observation available during the PAP. All efficacy analyses will be performed based on the mITT

population. Corresponding analysis will be performed for PP population for the primary efficacy endpoint. If the pure ITT (all randomized patients) population is different from the mITT population, we plan to perform a sensitivity analysis in this population as well to assess the robustness of the results.

2.5.1 Analysis of primary efficacy endpoint in PAP

The primary efficacy endpoint of change from baseline in FVC (% predicted) in upright position to Week 49 will be analyzed in the mITT population using MMRM with change from baseline as the outcome variable. The MMRM model will include the baseline FVC (% predicted) and age (both as continuous variables), gender (male or female), treatment group, visit, and treatment-by-visit interaction as fixed effects.

The analysis will include all post baseline scheduled assessments up to Week 49, regardless of treatment discontinuation status; missing data will not be imputed and will be assumed to be Missing at Random (MAR). Descriptive assessment of MAR assumption and sensitivity analyses to assess the impact of missing data are described in [Section 2.5.3](#).

An unstructured covariance matrix shared across treatment groups will be used to model the within-patient errors. The model will be fitted using restricted maximum likelihood. If the model does not converge with an unstructured covariate matrix, the following covariate matrix structures will be used in the order of heterogeneous Toeplitz (heterogeneous variance, an extension of homogeneous Toeplitz), homogeneous Toeplitz (equal variance and a separate correlation for each level of separation between the time points), heterogeneous AR(1) (heterogeneous variance, an extension of AR(1)), AR(1) (first-order autoregressive, equal variances and exponentially decreasing correlations). The first covariance structure yielding convergence will be used as the primary analysis.

The Kenward-Roger approximation will be used to estimate the denominator degrees of freedom. The difference between treatment groups will be estimated based on least-square means at the Week 49 visit within the MMRM model. A two-sided 95% confidence interval using the estimate and variance of the least-square mean difference will be provided.

Due to the small sample size within each country or region, the primary MMRM will not include region/country as a covariate. Also, since previous alglucosidase alfa studies did not suggest a baseline-by-visit interaction within either study treatment arm, the primary MMRM will not include the baseline-by-visit interaction in the model to improve statistical efficiency.

The primary analyses will be performed after all randomized patients have been followed for at least 12 months (49 weeks) after randomization (or discontinued the study follow-up early).

The primary statistical objective is to test the non-inferiority of avalglucosidase alfa versus alglucosidase alfa at two-sided 5% level of significance. The null and alternative hypotheses based on a non-inferiority margin of 1.1 are described as H_{01} and H_{a1} below:

H_{01} : avalglucosidase alfa–alglucosidase alfa \leq -1.1 versus H_{a1} : avalglucosidase alfa–alglucosidase alfa $>$ -1.1

If the lower bound of the two-sided 95% confidence interval for the difference of avalglucosidase alfa-alglucosidase alfa is larger than -1.1, the study will be considered to have met its primary objective and the non-inferiority of avalglucosidase alfa over alglucosidase alfa is established.

After non-inferiority is demonstrated, a test for superiority of avalglucosidase alfa versus alglucosidase alfa will be performed with an overall two-sided 5% level of significance.

The following SAS code will be used for the primary efficacy analysis:

```
ods output Diff = out1
      LSMMeans = out2;
proc mixed data = DATAIN method = reml;
  class TRT VISIT SEX USUBJID;
  model CHG_FVC = BL_FVC SEX AGE TRT VISIT TRT*VISIT/ ddfm = kr;
  repeated VISIT/type = un subject = USUBJID r;
  lsmeans TRT TRT*VISIT/cl diff;
run;
```

where TRT = treatment group, VISIT = (week 13, 25, 37, 49), SEX = (male, female), AGE = age at baseline (continuous), USUBJID = unique patient ID, CHG_FVC is the change from baseline in FVC (% predicted), and BL_FVC is the baseline FVC (% predicted) value.

The same analysis as described above will be performed for the PP population to assess the robustness of the study outcome.

A US FDA-specific exploratory analysis will be conducted using the method described above for those patients in the mITT population 8 years of age or older in order to match the lower age range of patients in the LOTS trial of alglucosidase alfa. This analysis will be used to support US approval.

In the case that both NI and superiority of FVC (% predicted) are demonstrated, a superiority test for 6MWT will be performed with a two-sided alpha of 0.05.

Note that the type I error is controlled for the primary endpoint of FVC (% predicted) in the above testing procedure. Analyses of secondary efficacy endpoints in PAP

The secondary efficacy endpoints for PAP are described in [Section 2.1.3.2](#).

2.5.1.1 Distance walked in 6MWT

2.5.1.1.1 Primary analysis of 6MWT based on distance walked

The primary statistical objective for 6MWT is to test the superiority of avalglucosidase alfa versus alglucosidase alfa at Week 49 in the mITT.

The change from baseline in total distance walked in 6MWT will be analyzed based on the MMRM model, similar to the primary endpoint described in [Section 2.5.1](#), assuming MAR. The

model will include the total distance walked in 6MWT at baseline, baseline FVC (% predicted) and age (as continuous variables), gender (male or female), treatment group, visit, and treatment-by-visit interaction as fixed effects. The difference between treatment groups will be estimated based on least-square means at the Week 49 visit within the MMRM model. A two-sided 95% confidence interval using the least-square mean difference and its variance will be provided. If the lower bound of the two sided 95% confidence interval for the least square mean difference of avalsuglucosidase alfa–alglucosidase alfa is greater than 0, then the statistical superiority of avalsuglucosidase alfa over alglucosidase alfa is established.

2.5.1.1.2 Additional supportive analyses for 6MWT

Additional supportive analyses related to the 6MWT endpoint are as follow:

- 6MWT % predicted change from baseline

The change from baseline in % predicted of the total distance walked in 6MWT will be analyzed separately based on the MMRM model, similar to the primary endpoint described in [Section 2.5.1](#). The model will include the % predicted distance walked in 6MWT at baseline, baseline FVC (% predicted) and age (as continuous variables), as well as gender (male or female), treatment group, visit, and treatment-by-visit interaction as fixed effects. A two-sided 95% confidence interval using the least-square mean difference will be generated in a similar way as the absolute distance in meters.

- Categorical response of 6MWT

Relative change from baseline in 6MWT for last observation within 49 weeks period for each subject will be categorized into <-15%, [-15%, -10%], [-10, -5%), [-5%, 0), [0, 5%), [5%, 10%), [10%, 15%), and ≥15%. The number and percent of patients within each category will be summarized by treatment group. Treatment difference will be tested with Fisher's exact test.

- Analysis of 6MWT based on subjects who completed the full 6 minute walk by excluding subjects that walked less than 6 minutes.
- Responder analysis
- The derivation of responder criteria for the 6MWT is complicated by the challenges associated with defining MCIDs for this outcome measure (27). Based on Redelmeier (27), 3 responder thresholds are currently proposed for 6MWT endpoint, similar to what was considered in previous LOTS study: 1) 54 meters (the estimated threshold), 2) 37 meters (the lower bound of the 95% CI of the estimated threshold and 3) 30 meters (the difference in 6MWT that result in patients feeling 'a little bit better' (27). In addition, a threshold of 27.5 meters is proposed based on a half of standard deviation of the change from baseline to Week 52 as observed in the previous LOTS study. A response will be defined as having a change from baseline in 6MWT distance of ≥54 meters, 37 meters, 30 meters, or 27.5 meters, respectively, based on Week 49 value. Patients without Week 49 assessment will be treated as non-responders. To compare the relative treatment difference for each of the response variable, an odds ratio (with 95% confidence interval)

for avalglucosidase alfa vs. alglucosidase alfa will be calculated based on logistic regression model with treatment group, adjusting for baseline 6MWT, age, and gender.

- Changes in use of assistive device

Number and percent of patients who have increased use of walking device (compared to baseline) will be summarized descriptively by study visit and treatment group. Time to increased use of walking device will be summarized using Kaplan-Meier estimate if sufficient number of patients reported increased use of walking device during the PAP.

When applicable, number and percent of patients with decreased use of assistive device compared to baseline will also be summarized descriptively by study visit and treatment group.

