1.3 DETERMINATION OF SAMPLE SIZE

Sample size calculations are based on non-inferiority test of the primary efficacy endpoint of change from baseline to Week 49 in FVC (% predicted) upright position, with the following assumptions:

Primary endpoint is normally distributed with a common standard deviation (SD) of 5.1% predicted, which is estimated based on the data from previous Phase 3, placebo-controlled LOTS trial (AGLU02704).

Mean treatment difference (avalglucosidase alfa–alglucosidase alfa) of 2.0% predicted, assumed based on a conservative estimate when comparing studies AGLU02704 and TDR12857 ([Section 1.3.2](#)).

A 2-sided 5% significance level,

Expected percent of missing data of up to 10% (estimated based on studies AGLU02704 and EMBASSY),

A non-inferiority margin of 1.1% predicted, which is based on the estimated alglucosidase alfa effect from the placebo-controlled study AGLU02704 ([Section 1.3.1](#)).

A total sample size of 96 (1:1 randomization ratio) will provide approximately 80% power to demonstrate non-inferiority of avalglucosidase alfa versus alglucosidase alfa, when the true treatment difference (avalglucosidase alfa–alglucosidase alfa) is 2.0% predicted. If the non-inferiority criterion is met, a test for superiority will be performed. If the true difference between avalglucosidase alfa and alglucosidase alfa is 3.6% predicted (see [Table 3](#)), the study will have more than 85% power to demonstrate superiority of avalglucosidase alfa to alglucosidase alfa.

Calculations were made using East 6.3 software.

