2.5.2 Multiplicity issues

A sequential test strategy for the primary efficacy endpoint and key secondary endpoints will be used to control Type 1 error rate at 5% in a strong sense. Testing will proceed according to the following order and will stop if there is a non-significant comparison:

1. The primary efficacy endpoint of FVC (% predicted) will be tested for NI of avalglucosidase alfa versus alglucosidase alfa first.
2. If NI is demonstrated, the superiority of the avalglucosidase alfa versus alglucosidase alfa in FVC (% predicted) will be tested with the same overall 5% significance level.
3. If the superiority of avalglucosidase alfa versus alglucosidase alfa is demonstrated on the primary efficacy endpoint, the hypothesis testing for the secondary efficacy endpoints will proceed according to the following order:
 - a) Change from baseline to Week 49 in total distance walked in 6MWT (a superiority test with a two-sided alpha of 0.05),

- b) Change from baseline to Week 49 in % predicted of MIP (a superiority test with a two-sided alpha of 0.05),
- c) Change from baseline to Week 49 in % predicted of MEP (a superiority test with a two-sided alpha of 0.05),
- d) Change from baseline to Week 49 in summary score of lower extremity strength by HHD (a superiority test with a two-sided alpha of 0.05).

Analyses of additional secondary endpoints will be considered for supportive purposes.

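### The supportive 6MWT category table is compared with Fisher's exact test, which is valid but ignores the order of its eight categories and gives up power against a shift

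*SAP*

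**What the plan says.** SAP section 2.5.1.1.2 opens with "Additional supportive analyses related to the 6MWT endpoint are as follow". The second item in its list is the category analysis: "Relative change from baseline in 6MWT for last observation within 49 weeks period for each subject will be categorized into" eight bands with cut points at −15, −10, −5, 0, 5, 10 and 15%. Counts and percentages per band are to be given by arm, and then "Treatment difference will be tested with Fisher" (the sentence goes on to name the exact test). No trend, rank or ordinal test is named for this table. As printed, the second band is closed at −10% and the third also begins at −10%.

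The 6MWT test that carries alpha is elsewhere. Section 2.5.1.1.1 specifies an MMRM on distance walked, and the sequence in section 2.5.2 lists "Change from baseline to Week 49 in total distance walked in 6MWT (a superiority test with a two-sided alpha of 0.05"). The category table is not in that sequence.

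**The concern.** The bands are a graded scale of worsening and improvement. Fisher's exact test on a 2 × 8 table (the Freeman-Halton extension) tests for any association: shuffle the eight columns and the p-value does not change. That has two consequences.

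- Evidence for a consistent shift is spread over 7 degrees of freedom instead of being concentrated on one.
- A significant result does not say which arm did better. The reader has to take that from the percentages.

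At stake is the usefulness of a supportive analysis for the key secondary endpoint. With a real but moderate benefit, this p-value could well be non-significant beside a positive MMRM, and so fail to lend the support it was planned to give.

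**Working it through.** **Sample size.** The plan states no power for this table. Its stated power is for non-inferiority on FVC: "A total sample size of 96 (1:1 randomization ratio) will provide approximately 80% power", with a "common standard deviation (SD) of 5.1% predicted", a difference of 2.0, a margin of 1.1 and two-sided 5%.

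- Per arm: n = 2(1.960 + 0.842)² × 5.1² / (2.0 + 1.1)² = 42.5, so 43.
- Total: 86 / (1 − 0.10) = 95.6, so 96.
- Noncentral t with 43 per arm gives 79.6%, as in SAP Table 4.

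So 43 per arm (10% missing) and 48 per arm (none missing) bracket the size. The category analysis uses the last observation within 49 weeks, so it should lie nearer 48.

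**Inputs the documents do not give.** There is no 6MWT treatment effect, baseline distance or SD of relative change. Section 2.5.1.1.2 describes 27.5 m as half an SD of the change in metres in the earlier placebo-controlled trial, so that SD is 27.5 / 0.5 = 55 m. Assumed for the simulation: normal relative change, control mean +2%, SD 10, 14 or 20%, and a pure shift in the experimental arm.

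**Simulation.** 1,500 trials per scenario with the SAP's cut points. Fisher's p-value was by Monte Carlo (1,000 draws); the comparator was a tie-corrected Wilcoxon test on the same categories. Relative loss = 1 − (Fisher power / Wilcoxon power). Ranges are over the three SDs.

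| Shift (SD) | 43/arm: Fisher | Wilcoxon | Loss | 48/arm: Fisher | Wilcoxon | Loss |
|---|---|---|---|---|---|---|
| 0.3 | 11–14% | 23–29% | 52% | 13–14% | 28–29% | 51–56% |
| 0.5 | 27–32% | 56–58% | 43–52% | 32–33% | 59–67% | 45–51% |
| 0.6 | 39–43% | 71–75% | 39–48% | 46–47% | 77–80% | 39–43% |
| 0.7 | 56–57% | 85–87% | 33–35% | 62–64% | 88–90% | 27–31% |
| 0.8 | 70–72% | 92–94% | 23–25% | 76% | 95–96% | 20–21% |
| 1.0 | 88–91% | 98–100% | 8–10% | 91–95% | 99–100% | 5–8% |

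With no shift, Fisher's test rejected in 4.7–5.7% of trials and Wilcoxon in 4.2–5.9%, so both hold about 5%. The simulation error on a power near 50% is √(0.25 / 1500) = 1.3 percentage points.

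**Asymptotic check.** At equal noncentrality, a 1-df test with 50, 80, 90 or 95% power corresponds to a 7-df test with 24, 49, 64 or 75%. The relative losses are 52, 38, 29 and 21%, the same pattern as the table.

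**In metres.** With 48 per arm and an assumed baseline of 400 m, the SD of relative change is 55 / 400 = 13.75%. Fisher against Wilcoxon power is then 40% v 71–74% for a 30 m shift (30 / 55 = 0.55 SD), 66–67% v 91–92% for 40 m (0.73 SD), and 94% v 99% for 55 m (1 SD).

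**The case against.** The best defence is that little depends on this p-value. The table is supportive, carries no alpha and has no decision rule. Directional 6MWT analyses are already planned: the MMRM on distance, the MMRM on percent predicted distance, and adjusted odds ratios for response at 54, 37, 30 and 27.5 m. The table's counts and percentages show direction whatever test is attached. Fisher's test is valid, and it can pick up patterns that a rank test may miss, such as more patients in both tails. The comparison above assumes a pure shift, the case that favours the rank test. For small shifts the rank test is weak too: 23–29% power at 0.3 SD.

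All of that stands, and it limits the weight of the point. It does not justify the choice of test, since the SAP frames the comparison as a treatment difference on an ordered scale and gives no reason to look for non-shift patterns.

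A reader might infer three stronger things that the documents do not support:

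- **That the test loses a fixed share of power, such as nearly half.** The loss runs from about 5% to 56% with the effect size, and the inputs needed to pick one value are absent.
- **That a non-significant result would contradict the 6MWT finding.** By sections 2.5.1.1.1 and 2.5.2, superiority is judged on the MMRM alone. Nor is non-significance always the likely outcome: Fisher's power is 66–67% at 40 m.
- **That the shared −10% boundary is an analysis flaw.** It matters only for a patient at exactly −10%, and may be a typing or text-extraction slip.

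**Conclusion.** The point holds in a conditional form. Eight ordered categories are compared with a test that ignores their order and does not indicate direction. If the treatment effect is a uniform shift, the relative loss of power against a rank test on the same categories is roughly 40–55% for shifts of about 0.3–0.6 SD, 20–35% at 0.7–0.8 SD, and about 10% or less near 1 SD. The SAP's own 27.5 m threshold is half an SD on the metre scale and so falls in the first range, but it is a patient-level response threshold, not an assumed difference between arms.

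The sizes rest on normality, the pure-shift assumption, the assumed SDs and 43–48 patients per arm. The qualitative point needs only the ordering of the bands. The consequence is an avoidable chance that a supportive table fails to support a real benefit. The primary endpoint, type I error, the testing sequence and the formal 6MWT conclusion are unaffected. This is a worthwhile improvement, not a defect in the trial's inference.

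**What to change.** In SAP section 2.5.1.1.2, replace Fisher's exact test for this table with one of:

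- a Wilcoxon-Mann-Whitney test on the ordered categories, a method the SAP already uses for FVC in section 2.5.3.2;
- a CMH row-mean-score test, with the scores stated;
- a proportional-odds model with the 6MWT covariates, which also gives a directional estimate with a confidence interval.

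Keep the counts and percentages. As a clerical tidy-up, write the second category as [−15%, −10%).

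The cost is one test name and one bracket, with no change to data collection, sample size or the testing sequence. If the primary-period data have already been unblinded, report the ordered analysis beside Fisher's test and label it post hoc.
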